## 7.2. Safety Analysis

Descriptive statistics on available patient characteristics (e.g., age, BMI, smoking and alcohol use, history of relevant medical diagnoses, use of relevant concomitant medications) will be reported for all exposure groups at baseline.

Incident cases of study endpoints will be included in the analysis. Women with a history of study outcomes recorded in the medical records prior to the index prescription will not be included in the primary analysis for that specific outcome, but will be analyzed separately. For example, a woman with a history of VTE prior to the index prescription will be categorized as a prevalent case and will be excluded from the primary VTE analysis. A

separate analysis for women with a medical history of VTE will be performed and the woman would remain eligible for the analysis of other outcomes as normal. Depending on the number of patients in these subgroups of prevalent cases of each endpoint, this supplemental analysis is likely to have low power to perform any statistical comparison and will be descriptive in nature.

Incidence rates will be calculated for all endpoints in all treatment groups; incidence rate ratios and 95% confidence intervals will be calculated and compared. Stratifications by risk factors of interest (e.g., age, BMI, history of selected medical comorbidities, selected concomitant medications) will be performed for each outcome depending on availability of the data. A multiple regression model may be fit for the primary objective of the study depending on the completeness of the data on potential confounders and accrual of a sufficient number of endpoints.

A time to event analysis may be conducted as a secondary analysis.

All analyses will be conducted for each country separately, as well as after pooling the data from all participating countries.

Given the rarity of certain malignancies in this population, the incidence rates observed in this study may be small and imprecise. In such case, to better characterize the rates obtained in this study, an additional analysis using external reference data for the malignancies may be conducted. The observed frequency of malignancies in all three treatment groups will be compared with the expected frequency calculated from an age and gender matched population-based reference group (e.g., GloboCan) This ratio of observed versus expected events and 95% confidence interval, will be reported.

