2 INTRODUCTION

Note: in this document any text taken directly from the protocol is *italicised*.

Osteoporosis is characterised by a decrease in bone mass and architectural deterioration of bone tissue. Subtle modifications of bone remodelling, related to abnormalities of bone turnover, can induce a substantial loss of bone over a prolonged period of time. A period of asymptomatic bone loss results in reduced bone strength. When bone loss is sufficient to cause mechanical weakness, fractures may occur spontaneously or as a result of minimal trauma. Osteoporotic fractures cause a substantial clinical and economic burden for society. Age and menopause are the two main determinants of osteoporosis. The cessation of ovarian production of estrogen, at the time of the menopause, results in an accelerated rate of bone loss in women.

Bazedoxifene (BZA) is a third generation non-steroidal selective estrogen receptor modulator (SERM) currently approved in the European Union (EU) for the treatment of postmenopausal osteoporosis in women at increased risk of fracture. BZA is an estrogen receptor ligand that exhibits tissue specific activity: BZA functions as an agonist in the bone and an antagonist in the breast and uterine endometrium. BZA was developed in tablet form and current dosing consists of once daily administration of a 20 mg tablet. BZA (Conbriza) was approved in Europe via the centralized authorization procedure in April 2009. The first EU launch occurred in Spain in September 2010 which was followed by launch in Italy in April 2011.

Currently, one other SERM, raloxifene (Evista®) is marketed in Europe for the treatment and prevention of postmenopausal osteoporosis.

Bisphosphonates are non-hormone compounds that bind to the bone surface and are then taken up by osteoclasts. Bisphosphonates have a profound effect on bone remodeling, and are widely used for the prevention and treatment of osteoporosis.

In clinical trials, BZA-treated women had an increased risk of venous thromboembolic events (VTEs) compared to placebo. VTEs are included in the product label as an important identified risk.

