* Due to low enrolment/accrual into the study, the original end of the study accrual period was extended from September 30th 2012 in Spain, and April 30th 2013 in Italy, to April 30th 2014 for both Spain and Italy. Extending the accrual period to April 2014 extended the study timelines by 1 year. The new accrual period for Spain is 43 months (October 1st 2010-April 30th 2014) and the new accrual period for Italy is 36 months (May 1st 2011-April 30th 2014).

Patients will be counted in according to the inclusion criteria.

Follow up for each endpoint will be from the index date to whichever of the following occurs first.

1. Endpoint under investigation
2. Last patient visit or completion of 5 years follow up, whichever occurs first.

Each patient will be followed for identification of selected endpoints for a period of up to five years from their index prescription date for BZA, bisphosphonate or raloxifene. The follow up will continue even if the woman discontinues the index medication or switches to a different medication during this five year follow up period. The follow up duration of an individual patient may be shorter than five years if the woman transfers out of the GP office that wrote the index prescription or if she dies.¹ In these situations the data will be censored on the date of last visit. This study will use the Cegedim Longitudinal Patient Database (LPD), an electronic medical records database. However, the Spanish and Italian databases of Cegedim Strategic Data (CSD) do not have recorded events of death and date of death. The discontinued patient's record indicate loss to follow-up for various reasons, such as patients' moving from the areas, patient's change of GPs or other various reasons. The number of patients who are lost to follow-up will be provided. A minimum of a six month history in the LPD database prior to the index date (at least one GP visit, whatever the motive of the visit to GP) is required for inclusion of population, in order to ensure a certain quality of information.

Study Population

The study population will be selected based on the following inclusion criteria and all eligible patients enrolled in this study will be included. No exclusion criteria were applied.

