5.4 SUBGROUPS

Age stratified randomly selected subgroup

In the current dataset, there are 1,823 patients in the bazedoxifene group and 82,041 patients in the bisphosphonate group. This means that there is more than 40 times the number of subjects in the bisphosphonate group compared to the number of subjects in the bazedoxifene group. To limit the number of patients in the bisphosphonate group, an age stratified random subgroup will be selected. Based on the sample size and relative risk estimates provided in the final study protocol (study protocol section 7.1, Sample size calculation), the 1,823 bazedoxifene subjects will be adequately matched by a ratio of 1:6 bisphosphonate subjects. Therefore $1,823 \times 6 = 10,938$ bisphosphonate treated subjects are needed to be randomly selected from the total of 82,041 bisphosphonate treated subjects.

Selection scheme: The age of subjects in the study will be categorized into 4 groups (45-49, 50-59, 60-69, and ≥ 70). In the bisphosphonate group, the percentage of subjects in each of these age groups is 1.4%, 13.7%, 28.7%, and 56.2% respectively. To maintain the same proportion of subjects in each age group for the bisphosphonate subgroup, there will be $1.4\% \times 10,938 = 153$ bisphosphonate treated subjects randomly selected from the 45-49 age group; $13.7\% \times 10,938 = 1,499$ subjects randomly selected from the 50-59 age group; $28.7\% \times 10,938 = 3,139$ subjects randomly selected from the 60-69 age group; $56.2\% \times 10,938 = 6,147$ subjects randomly selected from ≥ 70 age group.

Incident cases of study endpoints

Women with a history of study end points recorded prior to the index prescription will not be included in the analysis for that specific outcome, but will be analyzed separately as subgroups for each study end point. The analyses of the primary and secondary endpoints will be performed using these incident cases of study endpoints subgroups.

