For example, a woman with a history of VTE period prior to the index prescription will be categorized as a prevalent case and will be excluded from the primary VTE analysis. A separate analysis for subgroup of women with a medical history of VTE will be performed and the woman would remain eligible for the analysis of other outcomes as normal. Depending on the number of patients in these subgroups of prevalent cases of each endpoint, this supplemental analysis is likely to have low power to perform any statistical comparison and will be descriptive in nature.

Incident/new user subgroup

In this subgroup analysis, cohorts of incident and not prevalent users of bisphosphonate and raloxifene will be compared to a cohort of incident BZA users. Patients will be defined as incident/new user if they have not had any treatment for osteoporosis in at least 6 months prior to the index date. The index date for each patient is the date of the first recorded prescription for BZA or bisphosphonate or raloxifene during the study enrolment/accrual period.

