6.2 SAFETY ENDPOINTS

All the primary and secondary endpoints are safety endpoints (see below).

Primary Endpoints

- Venous thromboembolism (VTE) defined as deep vein thrombosis (DVT), pulmonary embolism (PE), retinal vein thrombosis, and sinus thrombosis

Secondary Endpoints

- Ischemic Stroke
- Thrombotic/Ischemic Cardiac Disorders (including myocardial infarction, myocardial ischemia and coronary occlusion)
- Atrial Fibrillation
- Hypertriglyceridemia

- Biliary Events: Cholecystitis, cholelithiasis
- Clinical Fractures
- Chronic/Acute Renal Failure (including chronic renal insufficiency and end stage renal disease)
- Depression
- Selected ocular events including retinal vascular occlusions, disorders of the globe, iris, ciliary body, retina, eye adnexa and cornea.
- Thyroid disorders
- Aggregate of all malignancies including Breast, Renal, Thyroid, Ovarian, Gastrointestinal tract, Lung cancer
- Malignancies of Breast
- Malignancies of Kidney
- Malignancies of Thyroid
- Malignancies of Ovary
- Malignancies of Gastrointestinal tract
- Malignancies of Lung

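### For fractures, the incident-case rule in SAP 5.4 treats the fracture that prompted treatment either as history or as a drug outcome, depending only on the date of its code

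*SAP*

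**What the plan says.** The rule is in SAP 5.4, under incident cases: women having the endpoint "recorded prior to the index prescription will not be included in the analysis for that specific outcome". Instead, they form a subgroup, one per endpoint, that is analysed on its own. Protocol 7.2 has the same rule for the primary analysis of each outcome: "Women with a history of study outcomes recorded in the medical records prior to the index prescription will not be included". The excluded women stay in the analyses of other outcomes. Of their separate analysis SAP 5.4 says, depending on numbers, that "this supplemental analysis is likely to have low power to perform any statistical comparison and will be descriptive in nature".

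The other provisions that bear on fractures are:

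- SAP 6.2 lists "Clinical Fractures" as a secondary endpoint, with no exemption from the rule and no definition of site or episode. The code lists are in a separate document (SAP 6).
- SAP 2.1 sets the outcome window: "Follow up for each endpoint will be from the index date to whichever of the following occurs first". The window closes at the endpoint, the last visit or five years. No lag after index is given.
- SAP 8.1.2 ends person-time at the date of diagnosis. It justifies one person-time definition for all endpoints on the ground that all are chronic diseases or malignancies with possible long latency.
- SAP 2.1 (Data Source) says that hospital care reaches the GP file at visits after discharge, and not systematically.
- Protocol 6.3 lists the endpoints whose records a clinical expert will review. Fractures are not among them.

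**The concern.** The rule suits a disease that begins once. A fracture is acute, can recur, and can be the reason for starting an osteoporosis drug. SAP section 2 gives the bazedoxifene (BZA) indication as "for the treatment of postmenopausal osteoporosis in women at increased risk of fracture", so some women may start treatment because of a fracture. For such a woman, the same clinical event is history if its code precedes the index prescription and an outcome if the code falls on that day or at a later visit. Only the date of data entry separates the two, yet in the second case an event that preceded the drug is charged to it.

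At stake is the fracture comparison in secondary objectives 2 and 3. Misplaced events raise the rate in every arm. If they are more frequent in one arm, the ratio partly reflects the reason for prescribing or the speed of coding. They would also gather soon after index, in current exposure and the shortest cumulative-exposure categories of SAP 8.1.3. The as-treated analysis would therefore not remove them.

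**Working it through.** **Tracing one fracture through the rules.** Suppose that a fracture leads to the index prescription.

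1. Code dated before index: the woman has a history, leaves the main fracture analysis and joins the descriptive subgroup.
2. Code dated on the index day: it is not prior to index, and follow-up has begun, so it appears to count. This is an inference; the SAP does not address same-day codes.
3. Code dated at a later visit: it falls inside the window, its date is the event date, and no stated lag, repeat-code rule or record review rejects it.

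The lists in SAP 8.1.1, 8.1.4 and 8.2.1 do not name prior fracture as a baseline item or covariate. The only fracture variable there is a hip, pelvis or leg fracture in the month before a VTE.

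**Size.** The plan has no fracture rate or precision figure to reproduce. What follows is an illustration with the true rate ratio set to 1.

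Inputs from the documents:

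- 1,823 BZA women and 1,823 × 6 = 10,938 sampled bisphosphonate women (SAP 5.4).
- Five years of follow-up (SAP 2.1) with 15% annual loss (Protocol 7.1). Person-time per woman is T = (1 + 0.85 + 0.85² + 0.85³ + 0.85⁴) × 0.925 = 3.709 × 0.925 = 3.43 years, giving half a year to women lost in a given year.

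Assumed inputs, not in the documents:

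- r, the true fracture rate: 10, 20 or 30 per 1,000 person-years.
- f, the share of women with a treatment-prompting fracture: 10% or 20%.
- q, the share of those fractures coded on or after index: 5%, 10% or 25%, the same in both arms.

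Of n women, n·f·(1−q) are excluded, n·f·q become events with about zero person-time, and n·(1−f) contribute n·(1−f)·T·r/1000 true events. The observed rate is therefore

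r + 1000·f·q / [(1−f)·T].

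*One arm.* For BZA with f = 20% and q = 10%: excluded 1,823 × 0.2 × 0.9 = 328; misplaced events 1,823 × 0.2 × 0.1 = 36; true events 1,823 × 0.8 × 3.43 × r/1000 = 50, 100 or 150. At r = 20 the observed rate is 20 + 20/2.744 = 27.3 per 1,000.

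*Same f and q in both arms.* The ratio is 1.00, but both rates are inflated.

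*Different f.* At r = 20 and q = 10%, with f = 10% for BZA and 20% for the comparator: (20 + 10/3.087) / (20 + 20/2.744) = 23.24/27.29 = 0.85. Over the grid, the first figure has f = 10% for BZA and 20% for the comparator, and the second has the reverse:

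| r per 1,000 | q = 5% | q = 10% | q = 25% |
|---|---|---|---|
| 10 | 0.85 / 1.17 | 0.77 / 1.31 | 0.64 / 1.56 |
| 20 | 0.91 / 1.09 | 0.85 / 1.17 | 0.74 / 1.36 |
| 30 | 0.94 / 1.06 | 0.89 / 1.12 | 0.79 / 1.27 |

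*Different q.* With f = 20% in both arms, r = 20, and q = 5% for BZA against 10% for the comparator: (20 + 10/2.744) / (20 + 20/2.744) = 23.64/27.29 = 0.87.

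*Cumulative incidence*, the main method in SAP 8.1.2, behaves alike. For the 0.85 case: BZA (18.2 + 112.6)/(1,823 − 164) = 7.88%; comparator (218.8 + 600.4)/(10,938 − 1,969) = 9.13%; ratio 0.86.

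**The case against.** The strongest reply is that the mechanism is inferred. The documents do not say how often a fracture prompts treatment. A GP who prescribes because of a fracture already knows of it and may code it at or before that visit. The database holds event dates (Protocol 3.2, SAP 2.1), so late entry need not mean a late date, and the separate code list might narrow the endpoint. This stands as a limit on the size. It does not close the gap, because the SAP does not say that an event date overrides the recorded diagnosis date and has no rule for codes on or just after index.

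Excluding women with the outcome in their history is also an ordinary incident-case design, and it limits confounding by recorded fracture history. That stands too, and is why the present analysis should be kept beside any new one. SAP 8.2.4 and 8.2.5 leave room for further covariates, but name none for fracture.

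A reader might infer three stronger claims that the documents do not support:

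- *That the rule removes the women for whom BZA is indicated.* The indication is increased fracture risk, which a woman without a recorded fracture can also have.
- *That fractures in the excluded women are lost.* They move to a separate analysis, although SAP 5.4 expects it to be descriptive.
- *That the bias favours one drug.* Protocol section 10 expects possibly healthier, younger raloxifene users. SAP 8.1.4 notes that bisphosphonate and raloxifene women may have been treated before enrolment, so their index may be a continuing prescription, whereas BZA was newly launched. These are reasons to expect the arms to differ, but they do not fix a direction for both comparisons.

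**Conclusion.** The concern holds for the fracture endpoint. The text gives one treatment-prompting event two opposite roles according to its code date, and nothing stated would detect or correct this. The reason given for a common person-time definition does not describe a fracture.

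Rate inflation needs only that some of these fractures are coded on or after index. Bias in the ratio also needs a difference between arms in f or q; without one the ratio is not shifted. The range of 0.64-0.94 or 1.06-1.56 rests wholly on the assumed r, f and q and a twofold difference in f, and is no forecast. It does show that modest late coding could matter.

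This is one secondary endpoint, so the change is advisable rather than essential. It would be wrong to read the point as a defect in the primary VTE comparison.

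**What to change.** Amend SAP 5.4 and 6.2 for fractures only:

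1. Treat a fracture code dated on the index day as history.
2. Start the fracture risk period, and its person-time, after a short fixed lag in every arm, for example 60 days, with no lag as a sensitivity analysis. State how a woman with a code inside the lag is handled.
3. Do not count a repeat code for the same fracture site where the codes allow site to be identified.
4. Report prior fracture by arm at baseline.
5. Add an analysis that keeps women with earlier fractures and adjusts for, or stratifies by, prior fracture. Report it alongside the present history-exclusion analysis.

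The cost is SAP wording and programming for one endpoint, with no new patients. The same-site rule depends on the detail in the ICD-9 and Spanish primary-care codes, and SAP 8.1 already expects some codes not to map. The lagged analysis will miss true fractures soon after index and same-site refractures. The 60 days is only an example; the length should be fixed before results by arm are seen.

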Any patient with a prescription for BZA (exposed cohort), raloxifene (comparator cohort) and bisphosphonate (comparator cohort) treatment accompanied with diagnosis of osteoporosis will be eligible when they meet other inclusion criteria. The detailed inclusion criteria will be as follows:

1. *Female*
2. *At least one prescription for BZA, raloxifene, or any bisphosphonate during the study inclusion period*
3. *A recorded diagnosis code of osteoporosis on or within 60 days prior to the index prescription date.*
4. *Age of patients ≥ 45 at the index prescription date*
5. *At least 6 months of follow-up data in the electronic medical record system prior to the date of index prescription.*

¹ The event of death and date of death are not recorded in CSD Italian and Spanish database. The discontinued patient's records indicate loss to follow-up for various reasons.

The applicability of the third criterion will be evaluated through performing a sensitivity analysis comparing those with osteoporosis diagnosis within 60 days and those without diagnosis within 60 days. This has become necessary due to a significant number of patients (> 45%) missing a recorded diagnosis of osteoporosis. If the venous thromboembolism rates of the two groups are comparable (i.e., difference within 20%), this criterion will not be included.

Data Source

This study will use the Cegedim Longitudinal Patient Database (LPD), an electronic medical records database that collects clinical data from primary care physician practices in the following European countries i.e., Spain, Italy, Germany, France, Belgium and UK. (In the UK the database is known as The Health Improvement Network (THIN).) For this study the Cegedim LPD in Italy and Spain will be used.

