Venous Thromboembolic Events (VTE) are defined as deep vein thrombosis, pulmonary embolism, retinal vein thrombosis, and venous sinus thrombosis. This objective is to compare this incidence in real life settings with validated diagnosis codes, ICD9 in Italy and International Classification of Primary Care (ICPC) codes in Spain.

The availability of medical history of all relevant medical diagnosis for patients will be checked in both the Spanish and the Italian database and presented if available. The variables of medical history (diabetes, hypertension, VTE and Malignancies) will be presented in classes (Yes/No) before index date. (All the detailed diagnosis codes of each endpoint have been validated by Pfizer and are available in a separate reference document). For all medical history and smoking status, if the relevant information is not found in the database, it will be assumed to be negative.

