8.1.2 INCIDENCE RATES

Incidence rates will be calculated for all endpoints in all cohort groups; incidence rate ratios and 95% confidence intervals will be calculated as specified previously.

The incidence rate for all end points will be calculated using both the cumulative incidence approach and an incidence density (person-time) approach. The cumulative incidence approach will be used as the primary analysis and it will be calculated as in the following formula:

$$\text{Incidence rate} = (\text{Total new cases during follow-up period} / \text{Total persons at risk during follow-up period})$$

For this study, the numerator will be defined as the total number of patients with a diagnosis of primary end points or secondary end points during follow-up period. The denominator will be the total number of all patients at risk in cohorts groups during follow-up period.

Secondly, an incidence density approach calculates time at risk in person-years, measured from first prescription to the end of the observation period. The incidence rate will be reported as per 1,000 person-years of observation as shown in the following formula:

$$\text{Incidence Rate} = (\text{Total new cases during follow up period} / \text{Total person years during follow-up period}) * 1000$$

The numerator will be defined as the total number patients with end points of interest during follow-up period. The denominator will be defined as the sum of person years of patients during the follow up period. For patients who have incidence of primary or secondary end points, person time will equal the sum of days from their first prescription of treatment (index prescription) until the date of the incident condition (diagnosis of primary or secondary end points). For patients who do not experience an incidence of primary or secondary end points, person time will equal the sum of days from their first prescription of treatment (index prescription) to the last visit date or completion of 5 years follow up at which all patients will be censored, whichever occurs first.

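### Endpoint history stops before the index prescription but follow-up starts on the index date, so a VTE code dated that day counts as incident even if it records an old event

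*SAP*

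**What the plan says.** **History.** SAP 5.4 gives the general rule: "Women with a history of study end points recorded prior to the index prescription will not be included in the analysis for that specific outcome". Its VTE example adds that "a woman with a history of VTE period prior to the index prescription will be categorized as a prevalent case". Protocol 7.2 has the same rule: "Women with a history of study outcomes recorded in the medical records prior to the index prescription will not be included in the primary analysis". The requirement that the history be recorded stands in the general rule and in the protocol, not in the VTE example. SAP 8.1.1 sets the same limit for the baseline flags, VTE among them, which "will be presented in classes (Yes/No) before index date".

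**Start of follow-up.** SAP 2.1: "Follow up for each endpoint will be from the index date to whichever of the following occurs first". SAP 8.1.2 counts a case's person-time "from their first prescription of treatment (index prescription) until the date of the incident condition". SAP 8.1.4 measures time to event from the index prescription date. The primary measure in 8.1.2 is cumulative incidence: cases during follow-up divided by persons at risk.

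**Index day for another code.** Inclusion criterion 3 does mention that day: "A recorded diagnosis code of osteoporosis on or within 60 days prior to the index prescription date".

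**Dating and review.** SAP 7 says that dates are recorded automatically. Protocol 3.2 and SAP 2.1 (Data Source) list event dates among the medical-history data. Protocol 2.2 and 6.3 require the records of potential VTE cases to be retrieved and reviewed by a clinical expert to confirm the diagnosis. The SAP does not mention this review.

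**The concern.** Put together, these rules leave the index day outside history and inside follow-up. No rule for that day, lag or onset-date rule corrects this. A VTE code dated on the index day thus counts in full in the primary numerator and adds no time at risk.

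First coding of an old VTE at the prescribing visit is plausible in this database. Only six months of prior data are required, hospital information reaches the GP file unsystematically (SAP 2.1), and unrecorded history is taken as absent (SAP 8.1.1). The SAP also notes of BZA that "VTEs are included in the product label as an important identified risk", which gives a GP a reason to ask about past VTE when choosing a drug.

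The primary comparison rests on few events, so a handful of misdated ones could shift the ratio. In a safety study, a shift towards no difference is the more troubling kind.

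**Working it through.** **1. The plan's own figure.** SAP 5.4 takes 1,823 BZA women and six times as many bisphosphonate women: 1,823 × 6 = 10,938. Its age strata agree: 153 + 1,499 + 3,139 + 6,147 = 10,938.

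**2. Other inputs.**
- VTE rate without a SERM: 1.74 per 1,000 patient-years (PY) (protocol 7.1).
- True incidence rate ratio (IRR): 2, one of the protocol's scenarios, and 1 for contrast.
- Mean follow-up per woman, T. The protocol gives up to 5 years and 15% annual loss but no mean. Loss at the start of each year gives 0.85 + 0.85² + … + 0.85⁵ = 3.15 PY; loss at the end of each year gives 1 + 0.85 + … + 0.85⁴ = 3.71 PY. The simpler 5 × 0.85 = 4.25 PY reproduces 22 of the 24 confidence limits in protocol Table 3 to one decimal. The range used is 3.15 to 4.25 PY, taken as equal in both cohorts.
- Share of women whose past VTE is first coded on the index day, q. **The documents give no figure.** The values 0.05%, 0.1% and 0.2% are assumptions.

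**3. Events without misdated codes.** Bisphosphonate: 10,938 × T × 0.00174 = 60.0 (T = 3.15) to 80.9 (T = 4.25). BZA at IRR 2: 2 × 1,823 × T × 0.00174 = 20.0 to 27.0.

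**4. Events added.** 10,938 × q = 5.5, 10.9 or 21.9 in the bisphosphonate group. In the BZA group, 1,823 × 0.1% = 1.8.

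**5. Observed ratio.** With r = 0.00174 × T:
- bisphosphonate only: IRR × r / (r + q)
- equal share: (IRR × r + q) / (r + q)
- BZA only: (IRR × r + q) / r

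For example, with T = 3.15, q = 0.1% and r = 0.00548, bisphosphonate only gives 2 × 0.00548 / 0.00648 = 1.69.

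Results at a true IRR of 2, for T from 3.15 to 4.25:

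| q (assumed) | Bisphosphonate only | Equal share | BZA only |
|---|---|---|---|
| 0.05% | 1.83–1.87 | 1.92–1.94 | 2.09–2.07 |
| 0.1% | 1.69–1.76 | 1.85–1.88 | 2.18–2.14 |
| 0.2% | 1.47–1.57 | 1.73–1.79 | 2.37–2.27 |

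At a true IRR of 1 and q = 0.1%: bisphosphonate only 0.85–0.88, equal share 1.00, BZA only 1.18–1.14.

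**6. Scale of the assumption.** 0.1% / 0.00174 per year = 0.57. So q = 0.1% means that about 0.57 years' worth of background VTE is coded on one day; q = 0.2% means about 1.15 years' worth.

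**7. Precision.** With exponential loss at 15% a year, T = (1 − 0.85⁵) / (−ln 0.85) = 3.42. Wald limits on the log ratio, with standard error √(1/BZA events + 1/bisphosphonate events), are then 1.23–3.25 at an undisturbed IRR of 2. With bisphosphonate only affected they are 1.06–2.76 (ratio 1.71) at q = 0.1% and 0.94–2.40 (ratio 1.50) at q = 0.2%.

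**The case against.** **The expert review.** Every potential VTE record is to be reviewed, and protocol 7.2 intends incident cases only. A reviewer could well spot an old event. This stands in part: the figures above take no account of review and so show what happens if it removes nothing. But the reviewer is asked to confirm the diagnosis, and an old VTE is a true VTE. Nothing tells the reviewer to establish onset or to move the woman to the prevalent group.

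**The date may be the event date.** If old events carry their own dates, the problem largely disappears. The documents do not settle it: SAP 7 points to automatic dating, the data listings to event dates.

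**The VTE example can be read more widely.** Without the word recorded, it could cover a past VTE whenever it was entered. The general rule in SAP 5.4 and protocol 7.2 is narrower, and a program will follow recorded dates.

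**The osteoporosis criterion is a different kind of rule.** It is an eligibility window for an indication, naturally coded when the drug is prescribed. That is fair. It shows only that the index day can be addressed explicitly.

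**Prevalent users.** The index date is the first prescription in the enrolment period, not the start of treatment. For a woman already on a bisphosphonate, the visit may be a renewal with no choice of drug, and an index-day VTE could reflect earlier treatment. This stands. A reader might infer that no index-day code can be a drug effect; that does not hold for these women.

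**Conclusion.** The gap is in the text: under the rules as written, an index-day VTE code is an incident primary event. Its effect is not established. The sizes rest on an assumed q, equal mean follow-up in both cohorts and no correction by review. At q = 0.1% and a true IRR of 2, the observed ratio is about 1.7 to 1.8 if only the comparator is affected and 1.85 to 1.88 if both cohorts are affected equally. The equal-share shift is small beside the protocol's own interval at this 1:6 ratio (1.3 to 3.1 in Table 3).

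A reader might infer that the rule biases the primary result in favour of BZA. The documents do not support that. Equal coding pulls a true IRR above 1 towards 1 but leaves an IRR of 1 unchanged. Excess coding among bisphosphonate users lowers the BZA ratio; excess coding among BZA users raises it. Steering of women with past VTE away from BZA is an inference from the label, and no direction can be predicted against raloxifene, another SERM. The point merits correction because the boundary is wrongly placed for old events and moving it is cheap, not because a bias has been shown.

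**What to change.** - **History.** In protocol 7.2, in both the general rule and the VTE example of SAP 5.4, and in the baseline flags of SAP 8.1.1, define endpoint history as recorded on or before the index prescription date.
- **Time at risk.** In SAP 2.1, 8.1.2 and 8.1.4, start it on the day after the index date.
- **Reporting.** Give the number of index-day codes by drug for each endpoint.
- **Sensitivity analysis.** Keep the present rule as one, so that any true index-day VTE, including one in a woman already on treatment, still appears in a reported result.

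It would also help to state whether the entry date or the event date governs.

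The cost is a phrase in each of these places, one date condition in the program and one extra table. The downside is that a rare true VTE diagnosed on the index day moves to the history group. If there are no index-day codes, the table will show it and the results will barely change.
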